1 PROTOCOL SUMMARY

1.1 SYNOPSIS

Participant Duration:	For pilot study – 9 months
Title:	MKit: A Pilot Study Testing a Life Skills Application to Address Interpersonal Relationships in College
Study Description:	This study utilizes implementation science principles to culturally adapt a pre-existing web-based application (WebApp) for use with college students. We will use the ADAPT-ITT process to adapt the WebApp to a diverse (race, ethnicity, gender/sexual identity) college population with a focus on life skills and holistic self-care as reinforcement to currently available primary prevention programming available to freshman students. Our hypothesis is that the adapted WebApp will be safe, acceptable, and students will be willing to use it as a reinforcement to current university primary prevention programming.
Objectives:	
• Primary: To evaluate the safety, usability, acceptability, and willingness of using the adapted WebApp among a randomized sample of 300 first year university students.• Secondary: To complete preliminary evaluations on efficacy measures such as sexual victimization/perpetration, rape myth acceptance, and power in sexual relationships to allow for power calculations for a future R-level submission.
Endpoints:	
• Primary: Safety (qualitative interviews), Usability (System Usability Scale, Brooke, 1986), Acceptability (investigator generated), and willingness to use (qualitative interviews).• Secondary: Sexual victimization/perpetration (Sexual Experiences Survey, Koss et al., 2007), Illinois Rape Myth Acceptance – Modified (McMahon & Farmer, 2011), Sexual Relationship Power Scale (Pulerwitz, Gortmaker, & DeJong, 2007)
Study Population:	300 first year university students (150 Control Group, 150 Intervention Group)
Phase:	Pilot
Description of Sites/Facilities Enrolling Participants:	University of Michigan Residence Halls (South and West Quad)
Description of Study Intervention:	Web-based app that uses a life skills approach to address healthy relationships and sexual violence.
Study Duration:	2 years 9 months

1.2 SCHEMA

1.3 SCHEDULE OF ACTIVITIES (SOA)

Procedures	Preparation before recruitment	Baseline	3-month follow-up	6-month follow-up	Post-study semi-structured interviews
Randomization by residence hall	X				
Demographics		X	X	X	
Healthy Relationship Knowledge Questions		X	X	X	
Illinois Rape Myth Acceptance Scale – Modified		X	X	X	
Sexual Experiences Survey		X	X	X	
Sexual Relationship Power Scale		X	X	X	
System Usability Scale			X	X	
System Acceptability			X	X	
User Data			X	X	
Reaction to content					X
Perceived safety					X
Desirability					X
Willingness for future use					X

2 INTRODUCTION

2.1 STUDY RATIONALE

There have been minimal attempts at providing reinforcement for students around the primary prevention of sexual violence and nobody has approached this topic with the consideration of holistic well-being in mind. Many of the currently available primary prevention programs include a one-time interaction and do not provide reinforcement throughout the student's college career (Banyard, Moynihan, & Plante, 2007; Foshee et al., 2004; Moynihan et al., 2015; Taylor, Mumford, & Stein, 2015; Taylor, Mumford, Stein, & Woods, 2015). Principles of learning suggest that attitude change and skill training are more effective with reinforcement (Skinner, 1958). There is a need for holistic interventions that provide students with the means to address all of the physical, emotional, and social changes they may be experiencing during their transition to young adulthood. Past research has emphasized that life skills and social competency are promising approaches that address individuals within their ecological context (Krug, Mercy, Dahlberg, & Zwi, 2002).

2.2 BACKGROUND

With a national annual incidence rate of 5%, rape is the most frequent violent crime that occurs on college campuses (Finn, 1995; Fisher, Cullen, & Turner, 2000). Nearly 80-90% of college students know the perpetrator, which increases the likelihood that the rape will be completed, rather than attempted (Fisher et al., 2000; Karjane, Fisher, & Cullen, 2005). Furthermore, many college survivors do not perceive or acknowledge their experiences as a rape, often because of lack of evidence, the absence of a weapon, or because alcohol and/or drugs were involved (Fisher, Daigle, Cullen, & Turner, 2003; Karjane et al., 2005). These characteristics of sexual assault in college therefore contribute to the underestimation, under reporting, under prosecution, and low rates of seeking post-assault services among college survivors (BonDurant, 2001; Karjane et al., 2005).

Despite the high prevalence of rape in the United States, an event with long-term negative effects on a survivor's health, few survivors receive comprehensive post-assault care. In the period immediately following a rape, about half of all survivors will have evidence of physical trauma, up to 30% contract a sexually transmitted infection (STI), and 5% of female survivors become pregnant (Resnick et al., 2000). Specific to college survivors, about 20% report physical injuries (Fisher et al., 2000), many fear social consequences so they alienate themselves from campus activities or drop out of school, and it appears that college women who experience post-traumatic stress disorder (PTSD) from an assault may use substances and/or sexual behavior to reduce distress (Messman-Moore, Ward, & Brown, 2009). Post-assault, survivors can access comprehensive health services through referral by rape crisis centers or via the emergency department from specially trained sexual assault nurse examiner (SANE) programs. Comprehensive care includes 1) treatment of physical injuries or other sequelae of the assault, 2) pregnancy prevention including options if emergency contraception is not effective, 3) STI screening and treatment, 4) psychological care for PTSD, 5) forensic and victim services, and 6) legal care including safety from the perpetrator and the ability to report the assault and press

charges if the survivor desires (Tjaden & Thoennes, 2006). However, only one in five women raped as an adult reported their rape to the police and of these reported rapes prosecution rates were only 37% (Tjaden & Thoennes, 2006). Thus, the prevalence of rape is under reported, under prosecuted, and many women do not seek care after experiencing rape due to multiple barriers to care (Munro, 2014).

Even with the high prevalence and severe physical health, mental health, and social outcomes associated with sexual violence, there are limited data available on effective primary prevention programs (Centers for Disease Control, 2016). A recent systematic review of primary prevention programs for sexual violence identified only three primary prevention strategies that have demonstrated significant effects on sexual violence including *Safe Dates*, *Shifting Boundaries*, and the 1994 Violence Against Women Act (VAWA) Funding (DeGue et al., 2014). However, there are promising trends that favor multisectoral programs that engage stakeholders to challenge the acceptability of violence and the underlying social risk factors. There is strong consensus among researchers that more rigorous evaluation of promising programs is needed in order to continue to address sexual violence (Ellsberg et al., 2015).

Furthermore, recent national legislation has also highlighted the need for primary prevention of sexual violence. The *Dear Colleague Letter* issued by the Obama Administration in 2011 recommended that institutions of higher education implement preventive education programs focused on sexual violence for incoming students. The 2014 VAWA prescribed more specific recommendations that new students and employees must be offered primary prevention and awareness programs focused on domestic violence, sexual assault, stalking, and rape. The 2014 VAWA acknowledged specific content that should be included in these programs but did not stipulate how these programs were to be administered to incoming students. Thus, each institute of higher education implements primary prevention programming individually, often using a combination of web-based, in-person, and performance based methods.

Many college campuses rely on online learning modules to meet the requirements of the 2014 VAWA; however, there is a lack of evidence on the effectiveness of these programs and the potential that mobile or web-based applications hold for the prevention of sexual violence. Technology has become a ubiquitous modality for communication and accessing knowledge across the United States. In 2011 the White House called for initiatives that leveraged technology to prevent dating and sexual violence (Rosenthal, 2013). This resulted in the creation of a mobile application called *Circle of 6* (<http://www.circleof6app.com/>), which makes it easy to contact a person in your circle to let them know where you are and what you need. More recently, a randomized controlled trial at a university in the Southeastern United States found a web-based bystander intervention approach, *RealConsent*, significantly reduced sexual violence perpetration and increased knowledge around consent, intervening, and rape myths and decreased negative attitudes around hostility toward women (Salazar, Vivolo-Kantor, Hardin, & Berkowitz, 2014). However, neither of these technology-based approaches targets the social and cultural constructions of sexual violence that promote gender inequality and discrimination nor do they offer holistic approaches to primary and secondary prevention (Dartnall & Jewkes, 2013).

A holistic approach recognizes college students as individuals transitioning into young adulthood. The transition into young adulthood is associated with myriad of preventable health problems including higher rates of mortality and more involvement in health risk behaviors (Ozer et al., 2012). Additionally, college students are often learning to manage school, work, new relationships, stress, conflict, and their own health for the first time as independent young

adults. A holistic approach aims to identify the student's goals and needs by increasing their ability to make decisions based on their personal values while also addressing communication skills in interpersonal relationships as an upstream approach to reduce sexual violence in the campus community. Positive and respectful communication within interpersonal relationships may help prevent some types of unwanted sexual activity. Furthermore, when students make decisions consistent with their values, they may be less likely to engage in behaviors or encounter situations where sexual assault perpetration or victimization could occur.

2.3 RISK/BENEFIT ASSESSMENT

2.3.1 KNOWN POTENTIAL RISKS

There is no more than minimal risk to the study subjects. There is a rare risk that a participant may experience emotional discomfort related to survey or semi-structured interview questions. All participants will receive resources to help alleviate any potential discomfort and will have the opportunity to skip any questions they choose. The rare possibility of breach of confidentiality exists. All data will be stored on a secure, HIPAA-compliant server and drive with monitored and controlled access to reduce this risk.

2.3.2 KNOWN POTENTIAL BENEFITS

The study participants will have the direct benefit of receiving information through a holistic, life-skills approach to addressing interpersonal relationships and sexual violence. This content may help them to navigate their own relationships.

2.3.3 ASSESSMENT OF POTENTIAL RISKS AND BENEFITS

The minimal risks associated with this study are reasonable given the potential impact of the project. The results of this study will provide the basis to scale-up this innovative intervention to reach a high-risk and vulnerable group, as college females are among those at the highest risk for sexual violence. This study therefore provides the opportunity to develop a low-cost/high-impact reinforcement intervention that could improve interpersonal relationships and reduce sexual violence within college campuses. As such, the available information suggests that the present clinical study has an acceptable risk-benefit ratio.

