Quad) at the University of Michigan will be randomized to receive either: (1) the control arm (n=150) which will receive usual care only (all incoming students receive three programs about healthy relationships and sexual violence including Haven, Relationship Remix, and Change it Up) or (2) the usual care (n=150) described above and the web-based intervention (MKit). We will use cluster-randomization by residence hall (to minimize contamination associated with individual-level randomization of students living in the same residence hall). Following the informed consent process, students in both conditions will complete a baseline survey of 85 questions. Baseline measures will include: 1) demographic data, 2) 20 items from the Sexual Experiences Survey (SES) will measure past experiences with sexual violence (Koss et al., 2007), 3) investigator developed questions on knowledge about sexual violence, 4) 22 items from the modified Illinois Rape Myth Acceptance Scale to measure attitudes endorsing rape myths (McMahon & Farmer, 2011), and 4) 6 items from the Sexual and Relationship Power Scale (SRPS) will measure the multidimensional nature of power in relationships (Pulerwitz & Barker, 2000). All of these are measures have been validated and used extensively in the United States to measure knowledge and attitudes related to gender based violence. Following the survey, students in the Intervention group will be given the opportunity to interact with the application at their own pace, choosing which content to view in the order they prefer.

The Control group will only receive the usual care delivered to all incoming University of Michigan students, which includes Haven (an online course about sexual violence), Relationship Remix (an interactive program about healthy relationships and sexual violence delivered by peers), and Change it Up (a theater based performance on bystander intervention). The Intervention group will receive the usual care described above as well as access to the adapted web-based application. They will be encouraged to interact with the web-based application throughout the study. Data will be collected on the content viewed by the participants, as well as the amount of time they spend within each content area, and the order in which they view the content.

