5 STUDY POPULATION

5.1 INCLUSION CRITERIA

For the pilot study, individuals who meet the following criteria will be considered eligible to participate in the study:

1. Currently enrolled as a student at the participating university
2. Participated in Relationship Remix in Fall 2017 as a first-year or transfer student
3. Willing to participate in the study
4. Able to speak and read English

For the semi-structured interviews, individuals who meet the following criteria will be considered eligible to participate in the study:

1. Currently enrolled as a student at the participating university
2. Participated in Relationship Remix in Fall 2017 as a first-year or transfer student
3. Participated in the pilot study
4. Willing to participate in the study
5. Able to speak and read English

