9.4.3 ANALYSIS OF THE SECONDARY ENDPOINT

Preliminary analyses of the survey data (sexual violence victimization and perpetration, rape myth acceptance, and sexual relationship power) will be analyzed using the Statistical Package for the Social Sciences (SPSS); all p-values will be set at $<.05$. Descriptive statistics will be assessed first. The baseline, 3-month post, and 6-month post-intervention tests will be examined for measures of central tendency, measures of dispersion, and frequency distribution on outcomes. Analysis of variance (ANOVA) will be utilized to determine if the scores on the baseline and follow-up tests differ significantly among the two arms. Usability and acceptability scores will be assessed among those in the intervention group.

We are not powered to assess outcome measures (sexual violence experiences/behaviors, rape myth acceptance, relationship power); however, we will look at the direction of effects for our outcome measures to allow for power calculations for future scale-up.

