9.4.5 BASELINE DESCRIPTIVE STATISTICS

Study groups will be compared on baseline characteristics, including age, race/ethnicity, gender, student group involvement, sexual orientation, and relationship status.

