9.4.7 SUB-GROUP ANALYSES

Primary and secondary endpoints will be analyzed based on gender, race/ethnicity, student group involvement, sexual orientation, and relationship status.

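### The overall comparison of the two halls is not adjusted for gender, so a different gender mix can tilt the direction of effect passed to the next study

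*Combined protocol and SAP*

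**What the plan says.** - **Premise.** Section 2.3.3 says "college females are among those at the highest risk for sexual violence". It gives no rate by gender and does not mention perpetration, rape-myth or relationship-power scores.
- **Allocation.** Sections 4.1 and 5.5 randomise two residence halls, one per arm, with "300 first year university students (150 Control Group, 150 Intervention Group" planned in the synopsis. Section 6.3 describes no stratification or matching and states that there is no blinding.
- **Entry.** Section 5.1 has no criterion or quota on gender; the main requirement is "Participated in Relationship Remix in Fall 2017 as a first-year or transfer student". Under section 5.5, intervention students receive a card leading to the app with an access code, and control students receive a link to the survey only.
- **Arm comparison.** Section 9.4.3, repeating 9.4.1, says "Analysis of variance (ANOVA) will be utilized to determine if the scores on the baseline and follow-up tests differ significantly among the two arms". It names no covariate or stratum.
- **Where gender appears.** Section 9.4.5: "Study groups will be compared on baseline characteristics, including age, race/ethnicity, gender". Section 9.4.7: "Primary and secondary endpoints will be analyzed based on gender, race/ethnicity".
- **Use of the result.** Sections 9.4.1, 9.4.3 and 9.4.9 say that the secondary outcomes are unpowered and that the direction of effect will support later power calculations. Section 3 calls data for those calculations a key part of the study.

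**The concern.** If an outcome differs by gender and the two halls differ in their share of women, the unadjusted arm difference contains a part that has nothing to do with the app. The halls are not balanced on gender. Volunteers in each hall also respond to different recruitment material, so the mix could differ for reasons beyond chance.

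The two places where gender is used do not remove this part. The baseline comparison describes the imbalance but prescribes no action. The subgroup analysis gives results by gender, but the plan does not say whether these are arm differences within gender, how they would be combined, or whether they replace the pooled contrast as the source of the reported direction.

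At stake is what this pilot hands on: the sign of the arm difference and the pooled event rates, both of which depend on who happened to volunteer in two buildings.

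**Working it through.** The plan gives no figure to reproduce: section 9.2 says that no formal sample size calculation was made. The documents also give no outcome rates by gender and no gender mix for either hall. What follows is an illustration under stated assumptions, with no app effect, 150 students per arm and students treated as independent.

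**Inputs**
- 150 per arm: synopsis and section 4.1.
- Overall 6-month victimisation of 2.5%: section 2.2 gives an annual rape incidence of 5%, and 1 − √0.95 = 0.0253. Applying a rape incidence to SES victimisation is an assumption.
- Split by gender (assumed, chosen to average 2.53% at 50:50): 4.0% in women and 1.06% in men, or 4.5% and 0.56%.
- Share of women in the two halls (assumed): 60% vs 45%, or 65% vs 40%.
- Gender difference on a scale (assumed): 0.3 to 0.5 SD.

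**Victimisation.** Arm risk = f × p(women) + (1 − f) × p(men), where f is the share of women. The standard error (SE) is √[a(1 − a)/150 + c(1 − c)/150] for arm risks a and c. The probability that the observed difference takes the sign of the gender-mix bias is Φ(difference/SE).

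Worked case: 0.60 × 0.040 + 0.40 × 0.0106 = 0.0282, and 0.45 × 0.040 + 0.55 × 0.0106 = 0.0238. The ratio is 1.19, the difference 0.0044, the SE 0.0184, and Φ(0.24) = 0.60. In counts, this is 4.2 against 3.6 expected events.

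| Rates, women / men | Share of women | Arm risks | Risk ratio | Difference (points) | SE (points) | P(sign follows mix) |
|---|---|---|---|---|---|---|
| 4.0% / 1.06% | 60% vs 45% | 2.82% vs 2.38% | 1.19 | 0.44 | 1.8 | 0.60 |
| 4.0% / 1.06% | 65% vs 40% | 2.97% vs 2.24% | 1.33 | 0.74 | 1.8 | 0.66 |
| 4.5% / 0.56% | 60% vs 45% | 2.92% vs 2.33% | 1.25 | 0.59 | 1.8 | 0.63 |
| 4.5% / 0.56% | 65% vs 40% | 3.12% vs 2.14% | 1.46 | 0.99 | 1.8 | 0.70 |

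Without imbalance the last column would be 0.50.

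**Higher rates.** SES victimisation may be more common than rape. With assumed rates from 5% / 1% to 20% / 5%, a 60% vs 40% mix gives a false difference of 0.8 to 3.0 points and a sign probability of 0.66 to 0.78. At 70% vs 30% these become 1.6 to 6.0 points and 0.79 to 0.94.

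**Scales, compared at follow-up only.** Bias = gender difference × gap in the share of women: 0.3 × 0.15 = 0.045 SD, up to 0.5 × 0.25 = 0.125 SD. The SE is √(2/150) = 0.115 SD. The sign probability runs from Φ(0.39) = 0.65 to Φ(1.08) = 0.86.

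**How large a gap is plausible by chance?** If both halls draw from a 50:50 population, the gap has an SD of √(2 × 0.25/150) = 0.058, or 5.8 points. Gaps of 15 and 25 points are 15/5.8 = 2.6 and 25/5.8 = 4.3 of these SDs. At a 5.8-point gap the risk ratio is only about 1.07 to 1.09 and the scale bias 0.02 to 0.03 SD.

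**Would the baseline comparison catch it?** At two-sided 0.05 (sidedness assumed), its power is about 94% for 60% vs 40% women and about 41% for 55% vs 45%. Detection changes nothing in the analysis, because no action is attached.

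**Events available.** 150 × 0.040 + 150 × 0.0106 = 6.0 + 1.6 = 7.6 expected victimisation events in 300 students.

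**The case against.** A reader might infer that the plan ignores gender. It does not. Sections 9.4.5 and 9.4.7 both use it, and the latter can reasonably be read to include arm differences within gender. The gap is narrower: the overall contrast is unadjusted, and nothing says how the gender results inform the reported direction.

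A reader might also infer that the protocol itself makes all these outcomes gender-dependent, so that false differences in victimisation and perpetration would run in opposite directions. Section 2.3.3 supports a gender difference for victimisation alone; the rest is assumption.

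The ANOVA is loosely specified. Section 4.1 calls the design before-and-after, so a change-from-baseline or time-by-arm reading is natural. Under it, a stable gender gap in the attitude scores cancels. This stands: the 0.05 to 0.13 SD bias applies to a follow-up-only comparison. For the SES, the baseline items cover past experiences and no recall window is given, so how far a baseline adjustment would help cannot be settled from the documents.

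Finally, chance dominates the victimisation result at the assumed rates, the outcomes are declared unpowered, and with one hall per arm every other hall difference stays confounded with treatment. All of this stands and limits the severity. It does not remove the case for using a covariate that is already collected.

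**Conclusion.** The point holds in limited form. The overall arm comparison is not adjusted for gender, the halls are not balanced on it, and the descriptive and subgroup uses of gender do not correct the pooled contrast.

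Under the main assumed rates and 15 to 25 point gaps, gender mix alone yields risk ratios of 1.19 to 1.46 for victimisation, and the observed sign follows the mix with probability about 0.6 to 0.7. For scales compared only at follow-up, the bias is 0.05 to 0.13 SD.

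The tempting stronger claim is that gender mix would decide the direction of effect. The figures do not support it in this range. The sign becomes close to certain only with something like 70% vs 30% women combined with a large gender difference in outcome. That gap is 40/5.8 = 6.9 chance SDs, and nothing in the documents indicates it. Even the 15 to 25 point gaps need a real hall or volunteer difference, which the different recruitment cards make possible but which is not documented.

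Severity is low: the endpoints are secondary and exploratory, and the primary endpoints are unaffected.

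**What to change.** Amend section 9.4.3 as follows.

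1. Include baseline gender as a covariate in the arm comparison of rape-myth and relationship-power scores.
2. For SES yes/no outcomes, use a Mantel-Haenszel risk difference stratified by baseline gender.
3. State in advance how sparse gender categories are pooled and how missing gender is handled. A stratum present in only one arm contributes nothing to the Mantel-Haenszel estimate, and participants may skip any question.
4. Take the reported direction of effect from the adjusted estimate, with its confidence interval.
5. For the power calculation, give gender-specific rates and SDs with intervals alongside the pooled ones, noting that SES counts by gender will be very small.
6. State that, with one hall per arm, this removes only the gender part of the hall difference.

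The cost is one model term and a few sentences, with no new data. On a scale with a 0.3 to 0.5 SD gender difference and a 50:50 mix, adjustment also removes about 2% to 6% of the variance: 0.0225/1.0225 = 2.2% and 0.0625/1.0625 = 5.9%. The downside is some instability in the SES strata.
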